5.7.3. Concomitant Radiotherapy

Palliative radiotherapy to specific sites of disease (eg, to a symptomatic solitary lesion or to the brain) is permitted if considered medically necessary by the treating physician and after consultation with the sponsor. All attempts should be made to rule out disease progression in the event of increased localized pain. It is suggested that the smallest radiation doses and smallest fields possible be used for palliation to minimize the inflammatory effects of radiotherapy. It is suggested that PF-05082566 and mogamulizumab treatment be interrupted during palliative radiotherapy, in consultation with the Sponsor.

5.8. Supportive Care

Palliative and supportive care for disease related symptoms may be administered at the Investigator's discretion and according to any available American Society of Clinical Oncology (ASCO) guidelines.

Patients should receive appropriate supportive care measures as deemed necessary by the treating investigator including but not limited to the items outlined in the following Sections.

5.8.1. Hematopoietic Growth Factors

Primary prophylactic use of granulocyte-colony stimulating factors is not permitted during the first 2 cycles of treatment but they may be used to treat treatment emergent neutropenia as indicated by the current ASCO guidelines.^[27]

Erythropoietin may be used at the investigator's discretion for the supportive treatment of anemia.

5.8.2. Anti-Emetic Therapy

Primary prophylaxis of nausea and vomiting is permitted. Nausea and vomiting should be treated aggressively, and consideration should be given in subsequent cycles to the administration of prophylactic antiemetic therapy according to standard institutional practice. Patients should be strongly encouraged to maintain liberal oral fluid intake.

5.8.3. Anti-Diarrheal Therapy

Patients may receive prophylaxis of treatment-induced diarrhea. Symptomatic care such as loperamide (Imodium[®]) is recommended. All patients who experience diarrhea should be advised to drink liberal quantities of clear fluids. If sufficient oral fluid intake is not feasible, fluid and electrolytes should be substituted via IV infusion.

5.8.4. Anti-Infective Therapy

Patients with a documented infectious complication should receive oral or IV antibiotics or other anti-infective agents as considered appropriate by the treating investigator for a given infectious condition, according to standard institutional practice.

5.8.5. Anti-Inflammatory Therapy

Anti-inflammatory or narcotic analgesic may be offered as needed assuming the drug is not included in [Section 5.7.1](#), Prohibited Concomitant Treatment. There is no anticipated risk of drug-drug interaction between mogamulizumab and PF-0582566.

Acetaminophen/paracetamol to a MAXIMUM total daily dose of 2 g is permitted. Daily intake over 2 g is prohibited.

5.8.6. Corticosteroids

Chronic, systemic corticosteroid use for palliative or supportive purpose is not permitted. Use of corticosteroids as symptomatic treatment may be allowed on individual basis and upon discussion with the Sponsor.

Acute emergency administration, topical applications, inhaled sprays, eye drops or local injections of corticosteroids are allowed and guidelines are provided in [Section 5.4.9](#).

5.8.7. Supportive Care Guidelines for Infusion Reactions to Either Study Drugs

Acute infusion reactions (which can include cytokine release syndrome, angioedema, or anaphylaxis) are different from allergic/hypersensitive reactions, although some of the manifestations are common to both AEs.

Signs and symptoms usually develop during or shortly after drug infusion and generally resolve completely within 24 hours of completion of infusion.

Signs/symptoms may include: allergic reaction/hypersensitivity (including drug fever), arthralgia, bronchospasm, cough, dizziness, dyspnea, fatigue/asthenia, lethargy, malaise, headache, hypertension, hypotension, myalgia, nausea, pruritus/itching, rash/desquamation, rigors/chills, sweating, tachycardia, tumor pain, urticaria (hives, welts, wheals) and vomiting.

In the event that a site does not have established procedures for the treatment of study drug associated infusion reactions, guidelines are provided in [Table 9](#).

Table 9. Infusion Reaction Treatment Guidelines for Either Study Drug

NCI CTCAE Grade§	Treatment	Premedication at subsequent dosing
Grade 1 Mild reaction; infusion interruption not indicated;	Continue infusion as per protocol. Increase monitoring of vital signs during the infusion as medically indicated until the patient is deemed medically stable in the opinion of the investigator.	To be considered upon Investigator discretion.
Grade 2 Requires infusion interruption but responds promptly to symptomatic treatment (eg, antihistamines, NSAIDs, narcotics, IV fluids);	Stop infusion and monitor symptoms. Appropriate medical therapy may include but is not limited to: IV fluid Antihistamines NSAIDs Acetaminophen Narcotics Increase monitoring of vital signs as medically indicated until the patient is deemed medically stable in the opinion of the investigator. If symptoms resolve within 1 hour of stopping drug infusion, the infusion may be restarted at 50% of the infusion rate (eg, from 100 mL/hr to 50 mL/hr). If symptoms last more than 1 hour after stopping infusion, dosing will be held. The patient should be monitored until symptoms resolve or is deemed medically stable in the opinion of investigator. Patients who develop prolonged symptoms (>24 hrs.) despite premedication should be permanently discontinued from further trial treatment administration.	Patients may be premedicated 1.5 h (±30 minutes) prior to infusion of mogamulizumab and/or PF-05082566 with: Diphenhydramine 50 mg PO or IV (or equivalent dose of antihistamine). Acetaminophen 500-1000 mg PO (or equivalent dose of antipyretic eg, paracetamol).
Grades 3 or 4 Grade 3; Prolonged (ie, not rapidly responsive to symptomatic medication and/or brief interruption of infusion); recurrence of symptoms following initial improvement; hospitalization indicated for other clinical sequelae (eg, renal impairment, pulmonary infiltrates) Grade 4: Life-threatening; ventilator support indicated.	Stop infusion. Appropriate medical therapy may include but is not limited to: IV fluids Antihistamines NSAIDs Acetaminophen Narcotics Oxygen Pressors Corticosteroids Epinephrine Increase monitoring of vital signs as medically indicated until the patient is deemed medically stable in the opinion of the investigator. Hospitalization may be indicated. Patient is permanently discontinued from further trial treatment administration.	No subsequent dosing

Note: Appropriate resuscitation equipment should be available in the room and a physician readily available during the period of drug administration

§Classified per the Common Terminology Criteria for Adverse Events v. 4.03 (CTCAE) at <http://ctep.cancer.gov>

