3.2. DLT Definition

Severity of AEs will be graded according to CTCAE version 4.03. For the purpose of dose escalation, any of the following AEs occurring during the DLT observation period (first 2 Cycles, ie, 8 weeks) that are attributable to one or both study drugs will be classified as DLTs:

Hematologic

- Grade 4 neutropenia lasting >7 days;

- Febrile neutropenia, defined as absolute neutrophil count (ANC) $<1000/\text{mm}^3$ with a single temperature of >38.3 degrees C (101 degrees F) or a sustained temperature of ≥ 38 degrees C (100.4 degrees F) for more than one hour;
- Grade ≥ 3 neutropenic infection;
- Grade ≥ 3 thrombocytopenia with bleeding;
- Grade 4 thrombocytopenia.

Non-Hematologic:

- Grade ≥ 3 non laboratory toxicities (excluding infusion reactions), except those that have not been maximally treated (eg, nausea, vomiting, diarrhea).
- Grade ≥ 3 laboratory abnormalities (other than AST/ALT) if:
 - Medical intervention is required to treat the patient, or
 - The abnormality leads to hospitalization.
- Grade 4 aspartate aminotransferase (AST) and alanine aminotransferase (ALT) increase.

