5.4. Administration

Study treatment administration should start no later than 7 days after registration.

A cycle is defined as the time from Day 1 dose to the next Day 1 dose of PF-05082566. If there are no treatment delays, a cycle will be 4 weeks in duration.

All trial treatments will be administered on an outpatient basis. After Cycle 1, study drugs may be administered up to 2 days before or after the scheduled treatment day of each cycle for administrative reasons. Patients will be observed in the clinic for at least 2 hours after the administration of study drug, throughout the duration of the study.

All patients should be weighed within 7 days prior to dosing for every cycle to ensure they did not experience either a weight loss or gain >10% from the prior weight used to calculate the amount of study drug required for dose preparation. Decision to recalculate the study drug dose based on the weight obtained at each cycle can be in accordance with institutional practice, however if the patient experienced either a weight loss or gain >10% compared to the weight used to calculate the initial dose, the amount of study drug required for preparation and administration for the current cycle must be recalculated using this most recent weight obtained.

As with any antibody, allergic reactions to dose administration are possible. Therefore, appropriate drugs and medical equipment to treat allergic or anaphylactic reactions must be immediately available, and study personnel must be trained to recognize and treat allergic and anaphylactic reactions. Patients should be instructed to report any delayed reactions to the Investigator immediately. If a patient experiences an infusion related reaction at any time during the study, premedication is recommended prior to subsequent infusions (see Section 5.4.2 for details on premedication to be used).

For both drugs, the exact duration of infusion should be recorded in both sources document and CRFs. The infusion rate should be reduced or interrupted in the case of symptoms of infusion reaction, and symptomatic treatment administered. The infusion may be continued at one-half the previous rate upon improvement of symptoms. If symptoms persist or worsen, the infusion should be discontinued.

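### Section 5.4, Table 8 and Table 9 of the protocol give conflicting instructions for infusion reactions with no order of precedence, and the one mandatory stop at Grade 3/4 depends on whether a site has its own procedures

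*Protocol*

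**What the plan says.** **Protocol Section 5.4 (Administration)** applies to both drugs at every site and names no grade. On symptoms, "The infusion rate should be reduced or interrupted in the case of symptoms of infusion reaction". Then: "The infusion may be continued at one-half the previous rate upon improvement of symptoms". If symptoms do not settle or get worse, that infusion is stopped. After any infusion reaction, premedication is recommended before later infusions.

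**Protocol Section 5.4.9.1, Table 8** covers treatment-related toxicity. The section calls it suggested guidance. Its non-hematologic Grade 3 and Grade 4 rows hold treatment until recovery and then lower the dose by one level. Permanent discontinuation is to be considered after a life-threatening event or failure to recover within 4 weeks. The Grade 3 row is limited to toxicity that remains despite maximal treatment; the Grade 4 row has no such limit. Neither row exempts infusion reactions.

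**Protocol Section 5.8.7, Table 9** is specific to infusion reactions.
- Grade 1: "Continue infusion as per protocol", with later premedication left to the investigator.
- Grade 2: stop; restart at half rate if symptoms clear within 1 hour, otherwise hold the dose.
- Grade 3 or 4: "Patient is permanently discontinued from further trial treatment administration", and no further doses.

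Section 5.8.7 introduces the table with a condition: "In the event that a site does not have established procedures for the treatment of study drug associated infusion reactions".

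**The concern.** A site faced with a severe reaction can find support in the protocol for more than one course: re-exposure, restart at a lower dose, or stopping for good. Nothing ranks the three texts. The strictest instruction is also the one whose application depends on local procedures that the protocol does not describe.

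The main stake is patient safety. Section 1.2.5.1 names infusion reactions as the most common non-hematologic toxicity related to mogamulizumab, and Section 5.8.7 says that they can include anaphylaxis.

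There is a secondary stake for the descriptive tables. SAP Section 3.5.1 makes infusion-related reactions an event of special interest. SAP Section 6.6.4 tabulates those leading to permanent discontinuation, and Sections 6.5.3.5 and 6.5.3.6 count infusion-rate reductions of 50% or more and infusion interruptions. A half-rate restart meets the 50% definition; an infusion continued unchanged does not. These counts would partly record which instruction was followed, not only how patients reacted.

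**Working it through.** **Step 1: the texts side by side.** There is no design figure to reproduce, so the main check is a comparison.

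| | Section 5.4 (all sites, no grade) | Table 8 (suggested, no exemption) | Table 9 (if the site has no procedures) |
|---|---|---|---|
| Grade 1 | Reduce rate or interrupt; later premedication recommended | No hold, same dose | Infusion continues; premedication at discretion |
| Grade 2 | Half rate on improvement, no time limit | Consider hold if recurrent or intolerable; same dose | Half rate only if cleared within 1 hour, otherwise dose held |
| Grade 3/4 | Half rate on improvement; stop that infusion if not settling; silent on permanent discontinuation | Hold, recover, restart one level lower; permanent discontinuation to be considered if life-threatening | Permanent discontinuation, no further doses |

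**Step 2: is there a tie-breaker?** None of these sections says that it overrides another. Table 9 is the more specific, but it is conditional. Its permanent-discontinuation sentence stands in the same column as the symptomatic treatments, so the condition on local procedures reaches the stopping rule as well as the choice of drugs.

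**Step 3: do other sections settle re-exposure?** Section 5.4.7 interrupts treatment for Grade 3 or 4 toxicity. Section 5.4.8 sets recovery criteria before re-treatment and says permanent discontinuation should be considered for a life-threatening event. Section 9.7 provides internal safety review and a dose-escalation committee. These are real safeguards, but none says whether a patient who recovers from a Grade 3/4 infusion reaction may be dosed again.

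**Step 4: how often might it arise?** Inputs:
- Grade 3 reactions on Day 1: 10 patients, 3.8% (Protocol Section 1.2.5.1).
- Drug-related Grade ≥3 reactions in the studies outside Japan: 4.6% (same section); 7/152 = 4.6%.
- Planned enrollment: about 70 overall (Protocol Summary), of whom 30 is the dose-finding maximum (Protocol Section 9.3).

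Expected number = n × p. Chance of at least one = 1 − (1 − p)^n, treating patients as independent with a common rate.

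| n | p | n × p | Chance of at least one |
|---|---|---|---|
| 70 | 0.038 | 2.66 | 0.934 |
| 70 | 0.046 | 3.22 | 0.963 |
| 30 | 0.038 | 1.14 | 0.687 |
| 30 | 0.046 | 1.38 | 0.757 |

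These are counts of patients with a severe reaction. The number for whom Table 8 and Table 9 actually collide may be lower, because Table 8's Grade 3 row excludes toxicity that resolves under maximal treatment.

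**The case against.** The best defence is that the texts overlap less than they seem to. Table 9 describes Grade 3 as prolonged, slow to respond, or recurring after improvement. Many such reactions fall under Section 5.4's instruction to stop the infusion, not its half-rate permission, which resembles Table 9's Grade 2 row. Table 8 is only suggested, its Grade 3 row is restricted, and it provides for sponsor consultation. At Grade 1, Table 9's category is by definition one where interruption is not indicated, and both premedication statements are non-mandatory.

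Much of this stands. It makes Grade 1 a lesser conflict and narrows the Grade 3 overlap. It does not remove the conflict. Stopping one infusion is not ending treatment, Table 8's Grade 4 row has no such restriction, and Section 5.4's ungraded premedication advice presumes later infusions that Table 9 rules out at Grade 3/4.

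A reader might also infer more than the documents support:
- **That these are the only safety rules for a severe reaction**, since Section 3.2 counts "Grade ≥ 3 non laboratory toxicities (excluding infusion reactions") as DLTs. Sections 5.4.7, 5.4.8 and 9.7 also act, and Section 3.1.9 lets the sponsor overrule an escalation.
- **That sites do handle reactions differently.** Local procedures are not in the documents, so only the possibility is shown.
- **That the TITE-CRM or the MTD is distorted.** The initial weights follow the share of the 8-week window completed, not exposure, and no effect on the MTD has been shown. SAP Section 5.2.2 pools centers, so no comparison between sites is planned.
- **That 14 to 24 of 70 patients are affected**, from any-grade rates of 20.4% and 33.9%. Those rates leave out the 81% in the Phase 1 study described in Section 1.2.5.1, and they count mild reactions where the conflict is minor.

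**Conclusion.** The concern holds as an internal contradiction in clinical-management text. The clearest conflict is at Grade 3/4, between Table 8's restart at a lower dose and Table 9's permanent discontinuation, with Section 5.4 silent on permanent discontinuation. The Grade 2 conflict over the 1-hour limit is real, and the Grade 1 conflict is lesser. Because Table 9 is conditional, the same severe reaction can be handled differently by site or by the section consulted.

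On size, about 2.7 to 3.2 of 70 patients would have a Grade 3 or Grade ≥3 reaction, with a 93% to 96% chance of at least one. This assumes that rates from T-cell malignancy studies of mogamulizumab carry over to solid tumors and to the combination, and that patients are independent. The documents do not establish either. No sample size or stated operating characteristic changes.

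**What to change.** Reconcile Section 5.4, Table 8 and Table 9. For each grade, state which text prevails. State also whether that text, including the Grade 3/4 instruction, applies at all sites or yields to local procedures, and add cross-references so that a reader of any one section reaches the same answer. Which clinical rule applies at each grade, and whether local procedures may replace it, is for the sponsor and investigators to decide.

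The cost is an amendment to protocol wording. It needs no new assessment, no extra patients and no change to the planned analyses. Sites with their own procedures would have to check them against the reconciled text.

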6. STUDY PROCEDURES

For screening, treatment period and follow up procedures, see [Schedule of Activities](#).

- Informed Consent must be obtained prior to undergoing any study specific procedure and may occur prior to the 28 day screening period.

For the treatment period discussed below, where multiple procedures are scheduled at the same nominal time point(s) relative to dosing, the following prioritization of events should be adhered to, where possible:

- Blood pressure/pulse rate – may be obtained prior to or after electrocardiogram (ECG) collection but must be obtained prior to blood specimen collection.
- ECGs – obtain as close as possible to the scheduled time, but prior to blood specimen collection and within 30 minutes of the nominal time.
- Clinical safety laboratory tests – obtain as close as possible to the scheduled time.
- Pharmacokinetic blood specimens obtain at the scheduled time.
- Other procedures – All other procedures should be obtained as close as possible to the scheduled time, but may be obtained before or after blood specimen collection, unless sampling is determined by the study personnel to potentially impact the results.

6.1. Screening

For screening procedures, see [Schedule of Activities](#) and [ASSESSMENTS](#) Sections.

Screening is to be performed within 28 days of registration. Tumor history includes information on prior regimens (including dosing and duration of administration, description of best response observed, recurrence date), surgery and radiation therapy. Medical history, includes history of other diseases (active or resolved) and concomitant illnesses.

6.2. Study Period

For treatment period procedures, see [Schedule of Activities](#) and [ASSESSMENTS](#) Sections.

The EOT assessments are to be performed 28 days (+7 days) after the last dose of study treatment. These assessments are to be performed if not completed during the previous week on study (during the previous 8 weeks on study for tumor assessments).

6.3. Follow-up Visit

For follow-up procedures, see [Schedule of Activities](#) and [ASSESSMENTS](#) Sections.

Patients continuing to experience treatment-related toxicity following discontinuation of study treatment will continue to be followed at least every 4 weeks until resolution or determination, in the clinical judgment of the Investigator, that no further improvement is expected.

Only those patients whose disease has not progressed at the end of treatment will enter into disease follow-up. During this follow-up period, patients will have disease assessments performed every 8 weeks \pm 7 days. Once patients have exhibited disease progression or began a new anti-cancer therapy (not including radiotherapy to a non-target tumor lesion), whichever occurs first, the date of progression or that of the new anticancer therapy initiation will be recorded on the appropriate CRF page, and the patients will be withdrawn from the study. No further data will be collected from these patients.

6.4. Patient Withdrawal

Patients may withdraw from treatment at any time at their own request, or they may be withdrawn at the discretion of the investigator or Sponsor for safety or behavioral reasons, or the inability of the patient to comply with the protocol-required schedule of study visits or procedures at a given study site.

Reasons for discontinuation of study treatment may include:

- Disease progression according to RECIST v. 1.1 ([Appendix 2](#)) and/or irRC ([Appendix 3](#)) (see [Section 5.4.5](#) for details and exceptions);
- Patients who have achieved a confirmed CR, and have had at least two additional cycles of mogamulizumab and PF-05082566 after the date the CR was confirmed;
- Global deterioration of health status requiring discontinuation;
- Unacceptable toxicity;
- Pregnancy;
- Significant protocol violation;
- Lost to follow-up;
- Patient refused further treatment (follow up permitted by the patient);
- Consent withdrawal (cessation of follow up);
- Study terminated by Sponsor;
- Death.

Reasons for withdrawal from study follow-up may include:

- Completed study follow-up;
- Study terminated by Sponsor;

- Start of another anticancer therapy;
- Refusal for further follow-up;
- Lost to follow-up;
- Death.

If a patient does not return for a scheduled visit, every effort should be made to contact the patient. All attempts to contact the patient and information received during contact attempts must be documented in the patient's medical record. In any circumstance, every effort should be made to document patient outcome, if possible. The investigator should inquire about the reason for withdrawal, request the patient return for a final visit, if applicable, and follow-up with the patient regarding any unresolved AEs.

If the patient refuses further visits, no further study specific evaluations should be performed, and no additional data should be collected. The Sponsor may retain and continue to use any data collected before such withdrawal of consent.

